### **Preparation/Storage**

Food preparation will take place in the CSIRO Nutrition and Health Research Clinic in line with the Food Risk Assessment Team (FRAT) guidelines. An application for FRAT approval will be submitted alongside this application for HREC approval. Meals will be delivered to participants homes by the student investigator. Food will be stored in cool bags with ice packs to ensure temperature control between preparation and delivery.

## **Data Collection and Analysis**

### **Dietary data**

Dietary data will be collected using an online diet diary application (Appendix 2). Details of this and instructions for use will be supplied at screening visits and participants will be instructed to record their dietary and fluid intake. Participants will be requested to complete the diary for 3 full days including one weekend day. Dietary data will be recorded between the screening visit and visit 2 and is designed to collect data representative of each woman's habitual diet.

### **Sample collection**

A 5-10mL sample of fore breast milk will be collected into a 10 mL polyprop vial and will be obtained by the mother by manual expression before breakfast in the morning. Further milk samples will be collected at hourly intervals in the same way. Samples will be collected by participants in privacy within their own homes. Mothers will be encouraged to express for a short time to collect the sample prior if timings coincide with baby feeding and will be discouraged from collecting milk from the opposite breast to the one baby is feeding on ('drip milk').

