### **Visit 2&3/Intervention (within participants' home)**

- Three main meals as well as snacks will be provided following specific diets (standardised/higher sugar). The meals may be tailored to personal preferences to a certain degree (allowing for all major food groups to remain included). Consumption at each meal will be measured by weighing anything not consumed at the end of the study day.
- Breakfast will be eaten when participants wake up, this will start the sample collection period. Lunch and dinner will be consumed at 5 and 10 hours from breakfast respectively. Snacks can be consumed at any time between meals and will be logged on a written document alongside fluid intake over the day.
- A 5-10mL sample of fore milk will be collected into a 10 mL polyprop vial and will be obtained by the mother by manual expression at hourly intervals in privacy within participants' homes.
- Women will be asked to record infant feeding times and duration.
- Record any adverse events, concomitant medication changes
- Babies will be weighed by the student investigator (or in the case of the Covid-19 safe protocol, scales will be provided for mothers to weigh their babies).

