### **Sample storage**

Following collection in 10 mL polyprop vials breast milk samples will be immediately frozen and stored at -20°C in participants' homes. Samples will be collected within 24 hours by the student investigator and transferred on ice to the laboratory where they will be stored at -20 °C until time of processing/analysis and thereafter. All laboratory assays will be completed in a batch once all samples have been collected. We anticipate samples will be stored for a maximum of 6 months prior to analysis.

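### Except at a feed, no rule sets which breast is sampled, and no side record is listed, so hourly samples cannot be linked to recent drainage of that breast

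*Protocol*

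**What the plan says.** All places are in the Protocol.

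- **Volume and vial.** Sample collection: "A 5-10mL sample of fore breast milk will be collected into a 10 mL polyprop vial". The list for visits 2 and 3 gives the same volume and vial.
- **Schedule.** The first sample is hand-expressed before breakfast, and then "Further milk samples will be collected at hourly intervals in the same way".
- **Choice of breast.** Guidance exists only for samples that meet a feed. "Mothers will be encouraged to express for a short time to collect the sample prior if timings coincide with baby feeding", and they "will be discouraged from collecting milk from the opposite breast to the one baby is feeding on". Nothing covers the other hours, and nothing links the breast used on one diet day to the breast used on the other.
- **Feed record.** Visits 2 and 3: "Women will be asked to record infant feeding times and duration". Side is not listed for feeds or for samples.
- **Freezing.** Sample storage: "Following collection in 10 mL polyprop vials breast milk samples will be immediately frozen and stored at -20°C". No fill limit is given.
- **Comparison.** Under Study Intervention, each woman receives both diets in random order and serves as her own control. Aim 2 is to assess variation across the day.

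**The concern.** The protocol treats the history of the sampled breast as relevant. It asks for fore milk, wants expression to come before a coinciding feed, and discourages drip milk from the other side. Those rules make sense only if composition may depend on what was recently drawn from that breast, or on how the milk was let down.

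The rules stop at the feed itself. With hourly sampling, many samples will fall between feeds. One of these may come from a breast emptied shortly before or from one that has rested. The feed log gives the time of the last feed but not its side, and the sample carries no side either, so the two cannot be joined.

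Two things are at stake. In the diet contrast, changes of side between the two days add within-woman variation that the paired design is meant to keep low. In aim 2, hour of day is not randomised. If feeds and changes of side follow a daily routine, an hourly pattern in milk composition could partly reflect drainage. The Background section says the pilot's apparent circadian pattern in protein and lactose needs confirmation, so this alternative explanation matters.

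Side must be noted at collection. No later analysis can recover it, and all assays are run in one batch after sampling has ended.

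**Working it through.** **1. What is fixed and what is left open**

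| Feature | Sample coincides with a feed | All other hours | Across the two diet days |
|---|---|---|---|
| Fraction, method, hourly timing | Fixed | Fixed | Same instructions |
| Breast sampled | Guided (encouraged, discouraged) | No rule | No rule |
| Side recorded | Not listed | Not listed | Not listed |
| Feed time and duration | Recorded | Recorded | Recorded |

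Linking a sample to recent drainage needs the time since the last feed and whether that feed was on the same side. The first is recorded and the second is not.

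**2. The plan's sample-size figure**

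Inputs from Statistical Power: paired design, 90% power, 1% significance, 13 dyads per age group, 20 recruited per group. The pilot difference is 5.36 g/dL, but the calculation used a smaller effect that is not stated. The SD of the paired difference is not stated either, so 13 cannot be reproduced forward. It can be solved backward for the standardised paired effect, dz (mean difference divided by SD of the difference):

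- Two-sided normal approximation: dz = (2.576 + 1.282)/√13 = 1.07.
- Two-sided noncentral t: dz = 1.25.
- One-sided, since sidedness is not stated: 1.00 (normal) or 1.13 (t).

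The allowance for loss is 1 − 13/20 = 35%.

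**3. What extra noise would cost (illustration)**

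The base case is two-sided t with dz = 1.25. Suppose unrecorded side and drainage add a fraction r to the variance of the paired difference. Then dz becomes 1.25/√(1 + r). The values of r are assumptions; the documents give nothing from which to estimate r.

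| r (assumed) | dz | Power, n = 13 | Power, n = 20 | n for 90% power |
|---|---|---|---|---|
| 0 | 1.25 | 90% | 99% | 13 |
| 10% | 1.19 | 87% | 99% | 14 |
| 25% | 1.12 | 81% | 97.5% | 16 |
| 50% | 1.02 | 72% | 94% | 18 |
| 100% | 0.88 | 57% | 85% | 23 |

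If both age groups are pooled for the overall diet contrast, 13 + 13 = 26 women keep about 95% power even at r = 100%.

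**4. Vial fill**

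The permitted fill is 5/10 = 50% to 10/10 = 100% of nominal capacity. Only the top of the range leaves no nominal headspace before freezing.

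**The case against.** The strongest reply is that both diet days follow the same instructions: fore milk, hand expression, an hourly schedule and the same vial. Diet order is random, and each day has many samples, so changes of side will partly average out. Recruiting 20 for 13 leaves room for some extra noise, and pooling the age groups leaves more. This stands for the diet contrast, where the problem is one of precision. It does not protect aim 2, because hour is not randomised and averaging over women does not remove a daily routine that they share.

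A second reply is that the side may be on a form not shown. The Covid-19 section mentions paperwork and instructions sent with the sampling materials. That is possible. The protocol's own list names only time and duration, so the item should be added there or confirmed.

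A reader might infer more than the documents support:

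- *That samples from the two days are not like for like.* The documents show only that comparability is not guaranteed.
- *That the 5 to 10 mL range distorts triglyceride.* The outcomes are concentrations, so volume does not enter them directly. The documents give no figure for how composition changes with the amount expressed.
- *That full vials overflow and lose fat.* A nominal 10 mL vial may hold more than 10 mL, freezing is immediate, and nothing ties any loss to one diet.

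**Conclusion.** The concern holds in a limited form. Outside feeds the protocol neither fixes the breast sampled nor lists side for recording, so hourly samples cannot be linked to recent drainage of the same breast. For the diet contrast the consequence is avoidable within-woman noise. No bias by diet is shown, and neither the planned sample size nor the error rate is shown to be wrong. For aim 2 the consequence is a possible confusion of feeding or side pattern with time of day, which could not be examined afterwards.

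The size is unknown. The power figures rest on assumed variance increases and on a two-sided t reading of the sample-size statement. Relevance also depends on composition varying with recent drainage, which the protocol's own collection rules imply but do not quantify. The fill range is a minor handling point. The whole is a cheap improvement, not a flaw that undermines the trial.

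**What to change.** In the visit 2 and 3 procedures and in Sample collection:

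1. Record the breast (left or right) for every sample and every feed, next to the feed times and durations already logged.
2. Ask the mother, where feeding allows, to sample the same breast at the same study hour on her second diet day as on her first. Keep the existing guidance for samples that coincide with a feed.
3. As a minor point, replace the volume range with one target inside it and below the vial's nominal 10 mL, because the vial is frozen at once.

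The cost is one extra log column, a slightly more demanding instruction for the mother, and less spare milk for the optional hormone assays.

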**Date of protocol: 20/01/2022**

## **Background**

Breast milk composition is believed to be highly variable due to an extensive array of factors which include maternal diet. Many previous studies have provided insights into the potential role of maternal dietary intake on the concentrations of key macronutrient (fat, protein and lactose) in human milk. These studies have suggested that concentrations of lactose, the most abundant carbohydrate (Smilowitz et al. 2013), are not affected by the maternal diet (Smilowitz et al. 2013 and Nommsen et al. 1991). Similarly, total protein concentrations in human milk are thought to be relatively stable, with some evidence even showing a compensatory ability for women to maintain consistent protein concentrations in their milk despite consuming diets low in protein (Lonnerdal 1986). Fats are known to be the most variable macronutrient in human milk, with many studies demonstrating that both the fat content and fatty acid composition of human milk shifts rapidly in response to changes in these factors in the maternal diet (Mohammed et al. 2009 and Henjum et al. 2018). However, there are significant weaknesses in the existing literature base, since the majority of these studies have measured effects on human milk composition in pooled samples collected over a 24-hour period before analysis. This means that they have no capacity to consider how milk composition varies over a day, or the effects of dietary changes on human milk composition in the short-term.

The design of the proposed research is based upon our recently published UK pilot study where 9 women were each given a control/higher sugar/higher fat diet over 3 separate days (Ward et al. 2021). On each of the 3 days breast milk was collected hourly for a period of 12 hours. The study showed a significant increase in breast milk triglyceride concentrations following a higher sugar diet, compared to a control diet ( $p < 0.001$ ). It was also identified that statistically significant variations in breast milk protein and lactose concentrations occurred across the 12-hour sampling period, indicative of a circadian rhythm that had not been previously reported. Given the novelty of the study protocol, and the study findings, it is important to confirm these in a larger group of women.

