## **Study Intervention**

The intervention within this study includes two different diets; one control and one higher in sugar. A cross-over design will be used where control and higher sugar diets will be provided in a random order to each woman across visit 2 and 3. Participants will be encouraged to try and avoid consuming foods other than those provided but can resume their normal eating habits once the last sample has been collected. If women consume anything other than the foods provided, they will be asked to record this information, similarly, if they do not consume all food provided they will be asked to retain the food for the student investigator to weigh and estimate the percentage of consumption at each meal.

There will be 7 days between these visits to allow for a washout period between diets.

There are no dietary restrictions during the washout period.

Participants will be discouraged from consuming caffeine or alcohol during the study period (i.e. days when intervention diets are being consumed).

The paired design means that in the analysis of the data each woman will act as her own control.

Considering dyads at two different infant ages will enable the project to address the third aim and determine whether milk composition varies across lactation and whether sensitivity to maternal diet may change over time.

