### **Statistical Analysis Plan**

Statistical analyses will be performed using SPSS software (version 21; IBM, Armonk, NY). Statistically significant differences in the variability of milk compositional concentrations will be determined using repeated and single measures ANOVA with Tukeys HSD post hoc tests where appropriate. A Bonferroni correction will be used to control for multiple comparisons. Statistical significance will be accepted with a *P* value of <0.05 and all results will be presented as mean with ± standard error of the mean.

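### The pre-breakfast milk sample precedes any study food but has no stated role in the analysis, and two Protocol sections do not agree that it comes before breakfast

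*Protocol*

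**What the plan says.** Protocol, Sample collection: the first fore-milk sample "will be obtained by the mother by manual expression before breakfast in the morning". It continues: "Further milk samples will be collected at hourly intervals in the same way". Nothing there sets the first sample apart from the later ones.

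Protocol, Visit 2&3/Intervention: "Breakfast will be eaten when participants wake up, this will start the sample collection period".

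Protocol, Statistical Analysis Plan: differences in milk concentrations are to be "determined using repeated and single measures ANOVA with Tukeys HSD post hoc tests where appropriate". The section lists no time points and mentions no baseline, covariate or change score.

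Protocol, Study Intervention: the two diets are given in random order and "The paired design means that in the analysis of the data each woman will act as her own control". On the interval between diets: "There will be 7 days between these visits to allow for a washout period between diets". Eating is unrestricted during that week.

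The number of samples per day is not fixed for this trial. For the pilot, whose design the trial follows, Background says: "On each of the 3 days breast milk was collected hourly for a period of 12 hours".

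**The concern.** Milk expressed before any study food has an expected diet difference of zero, apart from carry-over. If that sample is averaged with the later ones, the diet main effect over the day includes one value that the diet could not have changed, and the estimate is smaller than the post-breakfast effect.

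The same sample is also the only milk measurement of the woman's state at the start of each diet day. Her food on the preceding days is uncontrolled, and Background says that milk fat responds rapidly to diet. Differences between her two days in starting milk therefore go into the error unless the analysis uses the pre-breakfast value.

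The wording on when sampling starts matters separately. A woman who takes breakfast as the start of collection could give her first sample after eating, on one or both days. No later analysis can recover a pre-diet value that was not collected.

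**Working it through.** **Timing.** Under Sample collection, the first sample comes before breakfast. Under Visit 2&3, breakfast on waking opens the collection period. The two fit together if the woman wakes, expresses, eats and counts hours from breakfast. They do not if collection begins only once breakfast has been eaten. The Protocol does not say which is meant.

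**Inputs.**
- 13 dyads per infant-age group, 90% power, 1% significance, paired design; 20 per group recruited (Protocol, Statistical Power). Two-sided testing is assumed.
- Planning effect and SD of the paired difference: not stated. The pilot's increase of 5.36 g/dL is given, but the calculation allowed for a smaller effect.
- Samples per day: assumed to be 12 or 13, one pre-breakfast and k = 11 or 12 later, from the pilot's 12 hours.

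**The Protocol's own figure.** Without the planning effect and SD, 13 cannot be reproduced. It can only be inverted for d, the mean paired difference divided by its SD. Normal approximation: d = (2.576 + 1.282)/√13 = 1.07. Exact paired t-test (noncentral t, 12 df): d = 1.248. The exact value is used below.

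**Dilution.** An effect that is absent at 1 of k + 1 averaged samples is multiplied by k/(k + 1).
- k = 12: 12/13 = 0.923, a loss of 7.7%.
- k = 11: 11/12 = 0.917, a loss of 8.3%.

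**Power at 13 per group, two-sided 1%, SD held fixed.**
- k = 12: d = 1.248 × 0.923 = 1.152, power 83.9%.
- k = 11: d = 1.248 × 0.917 = 1.144, power 83.3%.

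The number needed for 90% power rises from 13 to 15 by the exact t-test. By the normal approximation it is 13 × (13/12)² = 15.3, so 16.

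The extra sample may also reduce noise. Let ρ be the share of within-woman variance common to all samples of one day. With k = 12, the diluted power is then 87.1% at ρ = 0, 84.7% at ρ = 0.2 and 84.2% at ρ = 0.5. The overall range is about 83 to 87%.

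**Power at 20 completers per group, same d and 1% level.** Diluted power is 98.1% (k = 11) or 98.3% (k = 12), against 99.4% undiluted.

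**Gain from covariate adjustment.** The standard error is multiplied by √(1 − r²), where r is the correlation between the baseline difference and the post-breakfast difference. The documents give no value of r, so these are assumptions:

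| r | Reduction in SE |
|---|---|
| 0 | none |
| 0.3 | 5% |
| 0.5 | 13% |
| 0.6 | 20% |

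**Change score compared with covariate.** Both use post-breakfast samples only (k = 12), 13 women and 1%; the unadjusted reference is 90%. Here r = ρ/√(ρ + (1 − ρ)/12).

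| ρ | r | Change score | Covariate (11 df) |
|---|---|---|---|
| 0 | 0 | 7% | 89% |
| 0.2 | 0.39 | 34% | 94% |
| 0.3 | 0.50 | 54% | 96% |
| 0.5 | 0.68 | 90% | above 99% |

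The change score breaks even only at ρ = 0.5. The covariate costs about one percentage point of power when the baseline carries no information.

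**The case against.** A reader might infer that the Protocol analyses the pre-breakfast sample as just another hourly outcome. It does not say so. Its analysis section lists no time points, and a separate statistical analysis plan, which has not been seen, could give the sample a baseline role. This stands: the dilution is conditional. It remains true that the Protocol's own analysis section fixes a method with no baseline in it, so a separate plan would have to add one.

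Keeping the sample as a time point is also defensible. The second aim is variation across the day, for which a morning value belongs in the series, and a pre-diet level helps a diet-by-hour interaction. This stands too; the dilution concerns only a diet main effect over all hours.

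A reader might further infer that the trial is underpowered. The documents do not support that. The effect size is back-solved. If the pilot's pooled estimate already included a pre-breakfast sample, nothing is lost against plan. The lower power applies at the minimum of 13 and the 1% level, not at 20 completers.

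Finally, an unadjusted within-woman comparison is valid in a randomised crossover, and one fore-milk sample may be a noisy baseline. Adjustment is therefore a matter of efficiency, and its benefit cannot be promised. The two timing statements can be read as compatible, but the text should not depend on that reading.

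**Conclusion.** The point holds in a limited form. A sample that cannot reflect the day's diet is collected on both days, the Protocol gives it no role in the diet comparison, and two sections leave open whether it precedes food.

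If it is averaged into a diet main effect, the effect is diluted by 7.7 to 8.3%, assuming 12 or 13 samples per day. Power at 13 per group would then be about 83 to 87%, provided that d = 1.248 and that the planning effect was purely post-breakfast. At 20 completers the loss is of little consequence. The precision available from the baseline ranges from nothing to a 20% smaller standard error over the assumed correlations.

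The effect is modest and its direction is known. The timing ambiguity is the more pressing part, because it has to be settled before samples are collected.

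**What to change.** 1. Reconcile Visit 2&3/Intervention with Sample collection so that both say that the first sample is taken before breakfast on both diet days, and state how many samples follow.
2. In the analysis section, name the pre-breakfast sample as that day's baseline. Keep it in the description of variation across the day.
3. Estimate the diet contrast from post-breakfast samples only, with the day's pre-breakfast value as a covariate. A model that constrains the two diets to equal means at baseline is an alternative and retains women with a missing baseline.
4. Do not use a simple change from baseline, which loses precision when the baseline correlates weakly with later samples.

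The cost is one line in the sampling instructions, a sentence or two in the analysis section and about one degree of freedom. No extra samples are needed. Settling this in advance also prevents a choice, after the data are seen, between including, excluding and adjusting for the sample.

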### **Sample storage**

Following collection in 10 mL polyprop vials breast milk samples will be immediately frozen and stored at -20°C in participants' homes. Samples will be collected within 24 hours by the student investigator and transferred on ice to the laboratory where they will be stored at -20 °C until time of processing/analysis and thereafter. All laboratory assays will be completed in a batch once all samples have been collected. We anticipate samples will be stored for a maximum of 6 months prior to analysis.

